### Efficacy endpoints

1. Components of the primary composite endpoint:
  - 3a Failed or no stent delivery
  - 3b Residual area stenosis  $\geq 20\%$
  - 3c Target vessel failure within one year
2. Components of target vessel failure at or before 1 year:
  - 4a Cardiac death.
  - 4b Target vessel-related myocardial infarction
  - 4c Clinically driven target vessel revascularization.
3. OCT endpoints
  - 5a Stent expansion at index procedure, MSA divided by the average reference area.
  - 5b In-stent late lumen loss up to 1 year, which is the decrease in MLA area from the index procedure

### 7.3.1 Secondary Safety Sensitivity Analyses

Just as in the main analysis, if there are missing values in any of the safety datasets, 1, 1a, 1b, 1c, 2, 2a, 2b, or 2c, we will report the best/worst case bounds Gabriel et al. [5]. There will be no additional sensitivity analysis for the secondary efficacy endpoints.

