## 6 Analysis Sets

- The “**Main analysis set A**” consists of all randomized participants who have a complete measure of the primary composite endpoint. This will exclude three groups of patients: patients who withdraw consent prior to 1 year and explicitly do not wish to participate in the 1-year clinical follow-up data collection, patients that are deemed to be lost to follow-up by the Clinical Endpoint Adjudication Board (see section 4.3 of protocol version 5.3), and patients who lack baseline OCT or Quantitative coronary angiography.
- The “**Sensitivity analysis set or Main analysis B**” consists of all randomized participants.
- **Secondary Safety endpoint analysis set 1, 1a, 1b, 1c:** consists of all randomized participants who have a measure of in-hospital and 1 year major adverse cardiac events for set 1, all randomized participants who have a measure of Cardiac death at or before one year after the index procedure, 1a, all randomized participants who have a measure of any myocardial infarction at or before one year after the index procedure, 1b, and all randomized participants who have a measure of stroke at or before one year after the index procedure, 1c.
- **Secondary Safety endpoint analysis set 2, 2a, 2b, 2c:** consists of all randomized participants who have a measure of in-hospital procedure events overall, 2, of periprocedural myocardial infarction, 2a, coronary dissection (beyond intended by lesion preparation), 2b, and coronary perforation/rupture, 2c. As it is very likely that all randomized participants will have measures of these events or be followed to know that the event did not occur, all of these groups may be the same as “Sensitivity analysis set or Main analysis B”

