### 7.1.2 Sensitivity Analyses

**For missingness** The main analysis is based on the “Main analysis set A”, which does not include patients for whom the primary endpoint is missing. This choice may be anti-conservative if the reason for drop-out was related to the outcome and differed between arms. For this reason, we will use the causal bounds from Gabriel et al. [5] for the effect given in equation 2 and the best-case/worst-case bounds equation 3 of the same paper if there are any missing composite outcome values based on “Main analysis set B” detailed in Section 6. If there is additional noncompliance, we will use the equivalent bounds for the per-protocol effect, as this can sometimes give large intervals. Given the conservative nature of the bounds, we will not further place confidence intervals on them unless it is deemed necessary for publication, in which case exact confidence intervals will be used.

**For mechanistic imputation** The composite outcome may have some form of “mechanistic” imputation, i.e. residual area stenosis  $>20\%$  is determined by direct measurement (OCT) of, if necessary, by quantitative coronary angiography. Values indicating residual area stenosis  $>20\%$  from OCT or angiography are considered reliable, however, particularly with quantitative coronary angiography, missing OCT analysis due to poor image quality or failure to obtain OCT is possible and may be related to residual area stenosis. Thus, we will impute all “mechanistic” imputed residual area stenosis that were found to be  $<20\%$  to be  $>20\%$  to determine the impact that missed OCT analyses could cause. Additionally, all patients without true measure of no event, that were adjudicated to have no event for the primary analysis, will instead be imputed to have an event and the impact of the adjudication will be determined by rerunning the primary analysis.

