## 7.3 Secondary Endpoints Analyses

For binary secondary safety endpoints we will use chi-squared tests, as we are more concerned with type II errors, i.e. not observing a true safety signal over making a type I error. Just as with the primary composite endpoint, we will never report findings for the secondary endpoints without the competing risk of death not included in the endpoint. For continuous outcomes we will use linear regression adjusting for site.

We will use the datasets numbered in the same manner as the safety outcome as detailed in Section 6 for each of the secondary safety analyses, as follows: The justification for this is that unlike efficacy secondary analysis that we would like to be comparable to the primary results and using the same dataset, for safety we will use all available data.

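### Section 7.3.1 triggers the safety missing-data bounds on datasets that, by definition, have nothing missing; it should name Main analysis set B

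*SAP*

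**What the plan says.** Three parts of the SAP bear on this.

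- **Section 7.3.1** is the only place that plans a missing-data sensitivity analysis for the secondary safety endpoints. It likens the check to the main analysis and then reports best/worst-case bounds "if there are missing values in any of the safety datasets, 1, 1a, 1b, 1c, 2, 2a, 2b, or 2c". It does not mention Main analysis set B.
- **Section 6** defines those datasets. Set 1 "consists of all randomized participants who have a measure of in-hospital and 1 year major adverse cardiac events for set 1". Set 1a is "all randomized participants who have a measure of Cardiac death at or before one year after the index procedure, 1a", and 1b and 1c follow the same pattern for myocardial infarction and stroke. The in-hospital family "consists of all randomized participants who have a measure of in-hospital procedure events overall, 2, of periprocedural myocardial infarction, 2a", and likewise for 2b and 2c. For the in-hospital sets it adds that practically everyone is expected to be measured, or followed well enough to rule the event out, so these sets may coincide with set B, which is everyone randomized.
- **Section 7.1.2** handles the same problem for the primary endpoint. The main analysis uses complete-case set A. The bounds are then applied "if there are any missing composite outcome values based on" set B.

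Section 7.3 explains the choice of safety datasets: "for safety we will use all available data".

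**The concern.** A participant without a measure of an endpoint is not a member of that endpoint's set. Looking for missing values inside the set therefore always finds none, and a programmer who follows the named datasets would have no reason to compute the bounds.

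At stake is the missing-data check for one-year major adverse cardiac events, cardiac death, myocardial infarction and stroke. Section 7.1.2 itself warns that dropping patients with a missing outcome can mislead when drop-out depends on the outcome and differs between arms. That reasoning applies equally to one-year safety, and the trial is open-label. Section 7.3 also says that, for safety, the authors worry more about missing a real signal than about raising a false one. A check that cannot start as worded works against that priority.

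**Working it through.** **Step 1: the condition against the definitions.** The plan gives no figure for this point, so the check is mainly one of logic.

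| Endpoint family | Set searched for missing values | Who is in that set | Missing values possible for its own endpoint |
|---|---|---|---|
| Primary composite (7.1.2) | Main analysis set B | all randomized | yes |
| One-year safety, 1 to 1c (7.3.1) | sets 1 to 1c | randomized and measured | none, by construction |
| In-hospital safety, 2 to 2c (7.3.1) | sets 2 to 2c | randomized and measured | none, by construction |

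If an in-hospital set does coincide with set B, that is because nobody lacks a measure. No bounds are then due under any reading. The rows where the wording matters in practice are 1 to 1c.

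**Step 2: what the bounds would show once set B is used.** Inputs:

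- N = 100 per arm: planned enrolment of 200, randomized 1:1 (Section 8).
- m participants per arm without the endpoint: an assumption, because the SAP gives no missing rate. The nearest figure is the enrolment margin in Section 8, 200 − 194 = 6, or 3 per arm if split equally. That margin was set for the primary endpoint and is not a stated loss rate for safety.
- e₁ and e₀: observed events in the IVL and conventional arms.

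Simple best/worst-case bounds for the risk difference are:

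- lower = e₁/N − (e₀ + m)/N
- upper = (e₁ + m)/N − e₀/N
- width = upper − lower = 2m/N

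With N = 100 the width does not depend on the event counts:

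| m per arm (assumed) | Width, percentage points |
|---|---|
| 2 | 4 |
| 3 | 6 |
| 5 | 10 |
| 10 | 20 |

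**Step 3: an illustration with hypothetical counts.** Take m = 3 and strokes in 3 of 97 IVL patients and 1 of 97 conventional patients.

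- Complete-case difference: 3/97 − 1/97 = 2/97 = +2.1 points.
- Lower bound: 3/100 − (1 + 3)/100 = −1.0 point.
- Upper bound: (3 + 3)/100 − 1/100 = +5.0 points.
- On the ratio scale, the complete-case value is 3.0 and the same two extremes give 3/4 = 0.75 and 6/1 = 6.0.

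With events this rare, a few missing patients are enough for the bounds to include both directions of effect.

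These are elementary bounds. The SAP takes its own from a cited paper that is not available here, and Section 7.3.2 refers to the risk ratio for binary secondary endpoints, so the reported form may differ.

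**The case against.** The strongest reply is that the sentence supplies its own remedy. It opens by tying the safety check to the main analysis, and there the procedure is unambiguous: analyse complete cases, then apply bounds from the same reference to outcomes missing among all randomized. Best/worst-case bounds have no purpose without participants who lack the outcome, so the literal reading would make Section 7.3.1 pointless. A careful analyst would probably use set B.

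Most of this stands, and it limits the consequence. A reader might infer that the safety bounds will never be produced and that harm could be hidden by differential loss. The SAP does not support that: the stated parallel with the main analysis makes omission unlikely, and nothing in the document points to appreciable differential loss.

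Three further limits are fair. Sets 2 to 2c are expected to be practically complete. Section 5 confines formal testing to the primary endpoint, so no confirmatory conclusion depends on these bounds. Section 7.3.2 adds cumulative incidence or Kaplan-Meier displays, which can use follow-up before loss, although they do not replace worst-case bounds and their dataset is not named.

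What the reply does not remove is the conflict itself. The section lists eight complete-case sets and never names set B, so the letter of the rule and its apparent intent give different instructions.

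**Conclusion.** The point holds as a minor drafting error. The trigger in Section 7.3.1 cannot be met as worded, because Section 6 defines the sets it searches by the presence of the measurement. This follows from the text and needs no numerical assumption.

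The practical effect is confined to the one-year endpoints 1 to 1c. Its size depends on missingness that the SAP does not state: 2m percentage points of risk difference for m missing in each arm of 100. The stroke example is illustrative, and the 6-point width for m = 3 should not be read as a figure from the plan. The primary endpoint's missing-data analysis is unaffected.

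**What to change.** Reword the condition in Section 7.3.1 along these lines:

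> If any randomized participant (Main analysis set B) lacks a measure of a safety endpoint, the best/worst-case bounds for that endpoint will be computed over Main analysis set B.

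The cost is one sentence. It uses the bounds method already planned for the primary endpoint, needs no new data, and leaves the main safety analyses and their datasets as they are.

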### 7.3.2 Additional Survival Analysis

For all binary event endpoints among the secondary endpoint in addition to the risk ratio of the endpoint and the risk difference of death from a cause not including in that particular event, we will display cause specific cumulative incidence using time to the endpoint. If there is not competing risks, these will instead be the kaplan-meier curves.

## 7.4 Exploratory Endpoints Analysis

For binary exploratory endpoints we will use the same exact testing as for the primary composite end point for binary outcomes and site adjusted linear regression for continuous outcomes. Multiple datasets will be considered, with the default data set being “Main analysis set A”, whenever possible. As some of the exploratory endpoints may have more missingness than the primary composite, when this is not possible the largest possible dataset will always be used.

There are several exploratory endpoints:

- Procedural endpoints
  - Complications (many)
  - Procedure details (durations/doses etc)
  - Procedure cost
- OCT endpoints at index procedure

- Stent expansion
- Stent malapposition
- Calcium disruption
- OCT endpoints at 1 year
  - In-stent late lumen loss
  - In-segment late lumen loss
  - In-segment re-stenosis
  - Stent malapposition
  - Quantification of neointima
- Symptom status at 1 year

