### 3.1.3 Exploratory

There are several exploratory endpoints:

- Procedural endpoints
  - Complications (many)
  - Procedure details (durations/doses etc)
  - Procedure cost
- OCT endpoints at index procedure
  - Stent malapposition
  - Calcium disruption
- OCT endpoints at 1 year
  - In-segment late lumen loss
  - In-segment re-stenosis
  - Stent malapposition
- Symptom status at 1 year

Here, we do not specify a hypothesis, as we will also not report p-values from any exploratory analysis.

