Note that the above statistical analyses will ignore that the randomization was stratified by site. This is usually not recommended, as this usually leads to a decrease in power as stratification variables are precision variables [3, 7]. However, our context is very specific, as we expect for there to be a low number of composite endpoint events, at least in the IVL arm. This has two important consequences. First, the loss of power is expected to be negligible. Second, ensuring proper type-I error control using a “covariate-adjusted” alternative approach is difficult using standard software. Additionally, the impact of not adjusting will be investigated as part of the Sensitivity Analyses.

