As part of the sensitivity analysis, we will adjust individually and collectively, if possible, for several variables known to be strongly predictive of the composite outcome but not used as stratifying variables for randomization. Thus, if by chance they are imbalanced in randomization, adjustment for them may reduce the effect of interest. In each regression, we will also adjust for site, with an indicator for each site that has at least three events and combining sites that are geographically close as needed when less than three events have occurred within a site. This will provide the correct standard error estimates since the randomization was stratified by site. For this reason, the results may be more significant or significant when the primary analysis is not, regardless of the results of the sensitivity analysis adjusting for site; this analysis will not replace the primary analysis in the publication as it does not strongly control the type I error rate. The additional variables include:

- Presentation (acute vs. chronic)
- Prior revascularization
- Diabetes mellitus
- LAD vs non-LAD

Logistic regression, including both main effects and interactions with treatment assignment, will be considered whenever possible; we will obtain marginal risk ratios via standardization (g-computation). Example code is provided in the code section 9.2. If this is not possible, i.e. the method will not converge due to the lack of events, we will run a main effect only model.

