## 8 Sample Size Determination and Power Calculation

In the protocol, it was stated that to reach 80% power to detect a true difference of 15%, with 25% in the standard of care group and 10% events in the IVL group for a two-sided test with alpha of 0.05, 194 patients total, 97 per arm, are needed when randomized 1:1. However, it was planned to enroll 200 patients to allow for a low level of loss to follow-up.

Instead, when using the intended exact method, we find that 194, 97 per arm, only provides 78% power for the hypothesized true difference in risks. Using the intended enrollment of 100 per arm, we reach the desired 80% power. These power calculations were carried out using the Power2x2 function, as outlined below.

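### Symptom status at 1 year is planned without adjustment for the baseline CCS or NYHA status listed in Table 1, so its estimate will be less precise than it could be

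*SAP*

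**What the plan says.** Section 7.4 lists "Symptom status at 1 year" among the exploratory endpoints and gives the whole list one rule: "use the same exact testing as for the primary composite end point for binary outcomes and site adjusted linear regression for continuous outcomes". The primary exact analysis (code in Section 9.2) has no covariates. The alternative for continuous outcomes has site only.

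Table 1 in Section 7.4.4 is a draft list of baseline variables. It includes NYHA above 2 and CCS above 2, each as a frequency and percentage. They are to be summarised by arm, without tests, and any imbalance that looks clinically important is to be remarked on.

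Prognostic covariates enter only in Section 7.1.2, as a sensitivity analysis of the composite, for "variables known to be strongly predictive of the composite outcome but not used as stratifying variables for randomization". The four named are presentation, prior revascularization, diabetes and LAD location, with site added. CCS and NYHA are not among them.

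On design, Section 7.1.1 notes that "the randomization was stratified by site" and mentions no other stratification factor. On inference, Section 3.1.3 sets no hypothesis for exploratory endpoints and adds that "we will also not report p-values from any exploratory analysis".

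**The concern.** Baseline symptom status is an obvious candidate predictor of symptom status a year later. If the two are correlated, a comparison that ignores the baseline value leaves explainable variation in the residual, and the confidence interval is wider than necessary. For this endpoint the estimate and its interval are all that will be reported.

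Symptom class is not described as a stratification factor, so the arms may differ on it by chance. Section 7.4.4 would have the authors remark on such a difference, but Section 7.4 gives them no planned way to act on it. They would either report an estimate that carries the imbalance or choose a covariate after seeing the data. In an open-label trial (Section 4.1), the second course is hard to defend for a symptom outcome.

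The SAP's own reasons for leaving out covariates do not transfer. Section 7.1.1 cites a low expected number of composite events and the difficulty of controlling type I error with adjusted methods. The first concerns the composite. The second has no bearing where no p-value is reported.

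**Working it through.** **The plan's own figures.** The SAP gives no figure for the symptom endpoint. Its only sample size figures concern the primary endpoint, with "25% in the standard of care group and 10% events in the IVL group for a two-sided test with alpha of 0.05". They were checked to confirm the working sample size.

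- "194 patients total, 97 per arm, are needed when randomized 1:1": the unpooled normal formula gives (1.960 + 0.842)² × (0.25×0.75 + 0.10×0.90) / 0.15² = 96.8 per arm, that is 97.
- "194, 97 per arm, only provides 78% power for the hypothesized true difference in risks", and 80% at 100 per arm: full enumeration of the unconditional exact test gives 78.2% and 80.3%. The ordering was by one-sided Fisher mid-p, taken to be the FisherAdj option.

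Both reproduce, and neither is affected by this point. The steps below use 100 per arm.

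**Inputs not in the SAP.** The correlation r between baseline and 1-year symptom status is assumed, from 0.1 to 0.6. For a binary outcome, the prevalence of CCS above 2 at baseline is assumed at 20% to 40%. The 1-year symptom risk is assumed at 20% to 50% in that group and 10% in the rest.

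**Step 1: continuous score.** Adjusting for baseline multiplies the residual variance by 1 − r² and the interval width by √(1 − r²). The unadjusted sample size that would match 200 adjusted patients is 200/(1 − r²).

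| r | Variance ratio | Width ratio | Narrowing | Equivalent unadjusted total |
|---|---|---|---|---|
| 0.1 | 0.99 | 0.995 | 0.5% | 202 |
| 0.3 | 0.91 | 0.954 | about 5% | 220 |
| 0.5 | 0.75 | 0.866 | about 13% | 267 |
| 0.6 | 0.64 | 0.800 | 20% | 312 |

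**Step 2: binary outcome.** Let p be the baseline prevalence, q₁ and q₀ the 1-year risks in the two baseline groups, and m = p·q₁ + (1 − p)·q₀. With no arm difference, the large-sample variance ratio after standardising over the baseline group is [p·q₁(1 − q₁) + (1 − p)·q₀(1 − q₀)] / [m(1 − m)].

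- Weakest case, p = 0.2, q₁ = 0.2, q₀ = 0.1: m = 0.12 and (0.032 + 0.072)/0.1056 = 0.985. Width ratio 0.992.
- Strongest case, p = 0.4, q₁ = 0.5, q₀ = 0.1: m = 0.26 and (0.100 + 0.054)/0.1924 = 0.800. Width ratio 0.895.

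The narrowing is therefore roughly 1% to 10%. These are large-sample ratios. They do not compare the adjusted interval with the exact one directly.

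**Step 3: chance imbalance.** With 100 per arm, the 95% limit for a chance difference in a standardised baseline score is 1.96 × √(2/100) = 0.28 SD. For CCS above 2 it is 1.96 × √(2p(1 − p)/100), which is 11.1 percentage points at p = 0.2 and 13.6 at p = 0.4. An imbalance of 0.28 SD shifts the unadjusted estimate by r × 0.28 SD: 0.03 SD at r = 0.1, 0.08 SD at r = 0.3 and 0.14 SD at r = 0.5. The half-width of the unadjusted interval is also about 0.28 SD, so at r = 0.5 an imbalance at the limit moves the estimate by half of it.

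**The case against.** The strongest reply is that nothing is wrong with the plan as written. An unadjusted randomised comparison is valid, the endpoint is exploratory, and no decision depends on it. That stands, and it is why the point is minor.

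Three stronger readings are tempting, and the SAP does not support them.

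- **Bias.** A reader might infer that a baseline imbalance would be mistaken for a treatment effect. Under randomization the unadjusted estimate is unbiased on average, and its interval already allows for chance imbalance. The shift in step 3 is conditional on the imbalance that happens to occur. Table 1 would also alert the reader to it.
- **Lost power.** Section 7.4 speaks of exact testing, so a reader might look for a power loss. Section 3.1.3 rules out hypotheses and p-values for exploratory endpoints. There is no target effect or decision rule to attach a power figure to, and only interval width is relevant.
- **A patient-reported outcome with widely varying baseline symptoms.** The SAP does not say who scores symptom status. It admits both stable disease and non-ST-elevation acute coronary syndrome but gives no distribution of symptoms.

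Two further objections limit the size of the gain. The SAP does not say that 1-year status is scored on CCS or NYHA; the protocol may. Table 1 shows only the cut at 2, so collection of the full class is likely but inferred. In addition, every patient is planned for PCI between the two measurements, which could weaken the correlation. At r = 0.1 the gain is negligible. None of this removes the point, because some precision is gained for any correlation large enough to outweigh the cost of one extra parameter.

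**Conclusion.** The point holds as one of efficiency. Section 7.4 leaves baseline symptom status out of the symptom comparison, and no other section of the SAP supplies it. The comparison remains valid and unbiased on average. The cost is a wider interval and an estimate that carries any chance baseline imbalance.

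The size rests on assumptions about the correlation and, for a binary outcome, about prevalence and risks. Across the ranges examined it runs from almost nothing to a fifth of the interval width for a score, and to about a tenth for a binary outcome. It also assumes that the 1-year measure matches one of the baseline measures. Primary and secondary conclusions are untouched. This is a worthwhile refinement, and the plan could stand without it.

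**What to change.** Add to Section 7.4:

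- Name the scale used for symptom status at 1 year (CCS, NYHA or both) and say whether it is analysed as a score or as a binary outcome.
- Analyse it with arm, site and the matching baseline measure as covariates, using the class or the cut at 2, on the scale used at 1 year.
- If it is a score, use linear regression with the baseline value added. If it is binary, use logistic regression with the standardization already set out in Section 7.1.2.
- Report the adjusted estimate with a 95% CI and no p-value, in keeping with Section 3.1.3, and keep the unadjusted result as supportive.

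The cost is a few lines of text and slightly more modelling. The baseline variables are already listed in Table 1. Sparse sites or classes may cause convergence problems. Section 7.1.2 already combines sites with few events and falls back to a main-effects model, and the same approach can be used here, with sparse classes pooled in the same way.
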